Secondary outcome measure: Interim naming. For naming prompts, the research assistant shows the child the post-book reading picture without the orthographic label and asks a question meant to elicit the phonological form of the target word (e.g., "What is the lightning doing?" to elicit flashing). Specific feedback is not provided but the correct orthographic label and context sentence always are provided after the child's response regardless of the accuracy of the response. This is shown in the scripts

https://asha.figshare.com/articles/Dose_Dose_Frequency_Storkel_et_al_2019_9745181. Naming responses were scored as correct or incorrect. Correct responses included the word itself (e.g., glared), the word in its bare form or with a different ending (e.g., glare, glaring) or an acceptable phonological substitution of the word (e.g., gwareing, judged on an individual basis). One independent judge scored naming responses and scores were verified by another judge.

Summary of the Design. The preceding figure provides a summary of the design. Upon meeting the selection criteria, children were randomized to 1 of 4 treatment arms. Pre-treatment definition testing was conducted for all 60 words, as indicated by the white box in Figure 1. Treatment 1 then was initiated for 30 words (Set 1 words with Set A or B being randomized to Set 1 or Set 2). Set 1 words were tested via naming and definition tasks four times during Treatment 1, as indicated by asterisks in the figure. Upon completion of Treatment 1, all 60 words (Set 1 and Set 2) were tested immediately and 2-weeks after treatment via the definition task. Note that Set 1 words have received treatment but Set 2 words have not yet received treatment and serve as untreated control words. Treatment 2 was then initiated for the remaining 30 word (Set 2 words). Set 2 words were tested via naming and definition tasks four time during Treatment 2, as indicated by the asterisks in the preceding figure. Upon completion of Treatment 2, all 60 words (Set 1 and Set 2) were tested immediately and 2-weeks after treatment via the definition task. Note that Set 2 words have just received treatment, whereas Set 1 words received treatment much earlier. Thus, for Set 1 words, these test points indicate longitudinal maintenance of learning following 5-12 weeks of treatment on a different word set.

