Data Analysis Strategy. A series of multilevel longitudinal models were evaluated using SAS Proc Mixed to describe the change in number of Set 1 and Set 2 words accurately defined over seven test points: pre-treatment, 36 exposures in Treatment 1 (i.e., last Treatment 1 session), immediate post-Treatment 1, 2-week post-Treatment 1, 36 exposures in the second treatment (i.e., last Treatment 2 session), immediate post-Treatment 2, and 2-week post-Treatment 2. Because the number of exposures varied for the interim definition tests, only the 36-exposure interim definition test data, which was consistent for all treatment conditions, were used. We expected significant slopes for Set 1 words during Treatment 1 when they were the target of intervention. We had no hypotheses about whether Set 1 words would decline or would be maintained after Treatment 1 ended and monitoring continued during Treatment 2. We expected non-significant slopes for Set 2 words during Treatment 1, when those words were not the focus of intervention, and significant slopes for Set 2 words during Treatment 2 when they were the target of intervention. Because the number of words defined were counts, the natural log of the words defined was modeled resulting in a model equivalent to a generalized linear mixed model with a negative binomial link function.

The significance of fixed effects was evaluated using Wald tests, and the significance of random effects was evaluated using likelihood ratio tests and information criteria between models with the same fixed effects. We evaluated models with time coded as days since the start of intervention as well as categorically by intervention point. The categorical model fit the data better. The final categorical coding of time is shown in Table 7. Because there were two treatment phases (Treatment 1 vs. Treatment 2) with different expectations for change in Set 1 versus Set 2 words in each phase, we examined a piecewise model of change in which the change related to the first treatment phase (i.e., pre-treatment, 36 exposures in Treatment 1, immediate post-

Treatment 1) was described by one linear slope and change related to the second treatment phase (i.e., 2-week post-Treatment 1, 36 exposures in the second treatment, and immediate post-Treatment 2) was described by a second linear slope. This allows the slope for each word set to differ across each phase, as predicted.

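### The plan states its Treatment 1 expectations as a significant slope for treated words and a non-significant slope for control words, and does not name the contrast between the two slopes

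*Combined protocol and SAP*

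**What the plan says.** The Summary of the Design gives the control its role. While Set 1 is treated, "Set 2 words have not yet received treatment and serve as untreated control words". Which books form which set is decided by chance: "Set 1 words with Set A or B being randomized to Set 1 or Set 2". The Randomization section likewise includes the assignment of Set A and Set B books in the randomization. Set 1 against Set 2 in Treatment 1 is therefore a concurrent, within-child, randomized comparison.

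The Data Analysis Strategy then states its expectations one set at a time. For treated words: "We expected significant slopes for Set 1 words during Treatment 1 when they were the target of intervention". For control words: "We expected non-significant slopes for Set 2 words during Treatment 1, when those words were not the focus of intervention". Of the piecewise model it says: "This allows the slope for each word set to differ across each phase, as predicted". On testing, it says: "The significance of fixed effects was evaluated using Wald tests". It names no set-by-slope interaction or contrast, and it gives no bound below which control growth would count as absent. It also states no alpha level or sidedness.

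**The concern.** A control is there to be compared with. The question it answers is whether treated words grew more than untreated words over the same period, and the answer is the difference between the two slopes with its confidence interval.

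A significant slope beside a non-significant one does not give that answer, for two reasons. The two estimates can fall on either side of the significance threshold and still be close together. A non-significant control slope may also be merely imprecise, and so compatible with real growth from repeated testing or maturation.

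What is at stake is the general claim that the treatment produces word learning. The Conclusion section still describes interactive book reading as promising for this purpose, and the untreated words are the design's concurrent evidence for that.

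**Working it through.** **Inputs.** The documents give no sample size, slope, standard error, correlation or alpha, so there is no figure of the plan's own to reproduce. Everything below is hypothetical: two-sided alpha 0.05 (critical value 1.96), equal standard errors unless stated, and a correlation ρ between the two slope estimates of 0, 0.5 or 0.7.

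**Step 1. A result that fits the expectations.** Take Set 1 z = 3 (significant) and Set 2 z = 1 (p = 0.317, not significant). With equal standard errors:

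z for the difference = (z1 − z2) / √(2 − 2ρ) = 2 / √(2 − 2ρ)

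| ρ | √(2 − 2ρ) | z for the difference | p | 95% CI for the difference, in SE units: 2 ± 1.96·√(2 − 2ρ) |
|---|---|---|---|---|
| 0 | 1.414 | 1.41 | 0.157 | −0.77 to 4.77 |
| 0.5 | 1.000 | 2.00 | 0.046 | 0.04 to 3.96 |
| 0.7 | 0.775 | 2.58 | 0.010 | 0.48 to 3.52 |

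The same pair of labels goes with no clear difference, a borderline one or a clear one. Which applies depends on a correlation that the labels do not carry.

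**Step 2. What the non-significant control slope leaves open.** In SE units the Set 2 interval is 1 ± 1.96, or −0.96 to 2.96. Its upper end almost reaches the Set 1 estimate of 3, so non-significance here does not show that control growth was absent.

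**Step 3. When the labels are enough.** The worst case is a Set 2 z just under 1.96. The difference is then certain to be significant only if

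z1 > 1.96 + 1.96·√(2 − 2ρ),

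which is 4.73, 3.92 or 3.48 at ρ = 0, 0.5 or 0.7. Above that value the labels do settle significance, and the contrast adds the size and the CI. The direct test is not always the harder one: with Set 2 z = 0 and ρ = 0.7, it needs only z1 > 1.96·√0.6 = 1.52.

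**Step 4. The two slopes may rest on different test points.** The Treatment 1 slope uses the pre-treatment, 36-exposure and immediate post-treatment tests, but the in-treatment tests in that phase are described for treated words only: "Set 1 words were tested via naming and definition tasks four times during Treatment 1". How much this matters depends on the time coding ("The final categorical coding of time is shown in Table 7"), and that table is not in the available text. In a simple least-squares slope the middle test has weight 0 under codes 0, 1, 2 and weight 0.5 under codes 0, 1, 1. If the slopes differ in precision, comparing their labels is less safe still.

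**The case against.** The strongest reply is that no error has been shown. The section speaks of what was expected. It sets no rule that efficacy will be concluded from one significant and one non-significant slope. The model lets slopes differ by set, and fixed effects were Wald-tested. If both sets are in one model, the set-by-slope term may already be among those tests. The text is a short summary that refers to a publication for full results. All of this stands, and it limits the point to a contrast that is not named.

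A reader might infer more in three ways, and the documents support none of them.

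- **That the treated-versus-control difference was never tested.** The text does not settle this either way.
- **That the plan has an inflated false-positive rate.** If both sets truly grew equally, with 50% power for each slope and zero correlation, the two-part pattern would arise in 0.5 × 0.5 = 25% of trials, against 2.5% for a direct test in that direction. But no decision rule is stated, and nothing indicates equal growth. The peak falls to 16.7% at ρ = 0.5 and 12.7% at ρ = 0.7, and there is no inflation if neither set grows. The 25% is not an error rate of this trial.
- **That the main result is in doubt.** The stated purpose is to study dose, dose frequency and predictors of response. All four arms are treated, and this contrast does not enter the comparison between them. The reported finding that children learned words during treatment is a within-treatment statement and does not itself claim superiority over control words.

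What remains is that allowing slopes to differ is not the same as testing whether they do. The two labels are the only treated-versus-control expectation that the plan states for Treatment 1.

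**Conclusion.** The point holds as a gap in specification and reporting. The design supplies a randomized concurrent control, and the plan does not name the contrast that would use it. Neither the pair of significance labels nor the non-significant Set 2 slope can replace that contrast.

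The size cannot be known from the documents. The illustrative p-values of 0.157, 0.046 and 0.010 rest on assumed z values, equal standard errors, two-sided alpha 0.05 and assumed correlations. If the Set 1 effect is large enough (z above about 3.5 to 4.7 under those assumptions), the practical gain is limited to the size of the difference and its CI. The point bears on the general statement that the treatment produces learning, not on the dose and dose-frequency conclusion. It is worth acting on because the remedy is cheap, not because a wrong result has been demonstrated.

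**What to change.** 1. Base any statement that treated words grew more than untreated words on the Treatment 1 set-by-slope contrast, Set 1 minus Set 2. Take it from a model that contains both word sets. The section refers to a series of models, so if the sets were fitted separately, refit them jointly.
2. Report the contrast with a 95% CI on the model scale. Give it as a ratio only if the handling of zero counts allows it: the section models the natural log of the counts and does not say what was done with zeros. If a constant was added, the exponentiated contrast is not a ratio of words defined.
3. Report the Set 2 Treatment 1 slope as an estimate with a CI, and do not rely on its non-significance.
4. State whether the contrast was part of the reported analysis. If not, label it post hoc.
5. Optionally, add a sensitivity fit on the pre-treatment and immediate post-treatment tests, which both sets share.

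The cost is one contrast, one interval and some wording, with a small joint refit if the sets were modelled apart. No new data are needed. The reported effect may be smaller once control growth is subtracted, and a contrast added now carries less weight than a prespecified one.

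### Learning of Set 2 words is judged by a non-significant slope followed by a significant one, with no stated test of the difference between them

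*Combined protocol and SAP*

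**What the plan says.** Summary of the Design sets out a staggered scheme. "Pre-treatment definition testing was conducted for all 60 words". Then "Treatment 1 then was initiated for 30 words" (Set 1), and the other 30 (Set 2) were taught in Treatment 2. At the two test points after Treatment 1, "Set 2 words have not yet received treatment and serve as untreated control words". After Treatment 2, the Set 1 results are described as showing "longitudinal maintenance of learning following 5-12 weeks of treatment on a different word set".

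Data Analysis Strategy gives the criteria. For the second set, "We expected non-significant slopes for Set 2 words during Treatment 1, when those words were not the focus of intervention"; the same sentence goes on to expect "significant slopes for Set 2 words during Treatment 2 when they were the target of intervention". For the first set in the later phase, "We had no hypotheses about whether Set 1 words would decline or would be maintained after Treatment 1 ended". Fixed effects are judged by Wald tests; the text gives no null value, alpha or sidedness. The piecewise model gives each word set its own slope in each phase. The first slope covers the pre-treatment, 36-exposure and immediate post-Treatment 1 points. The second covers the 2-week post-Treatment 1 point, the 36-exposure point of Treatment 2 and the immediate post-Treatment 2 point. No contrast between slopes is stated. Summary of Results reports significant word learning under every dose format.

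**The concern.** Once Treatment 2 starts, every target word has been or is being taught, so nothing shows what would have happened to an untaught word over the same weeks. Set 1 cannot fill the gap: those words were taught, no course is predicted for them, and Summary of Results reports significant forgetting after treatment is withdrawn. Using Set 1 as the reference could therefore make Set 2 gains look larger.

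The remaining evidence is the pair of Set 2 slopes. One significant and one non-significant result do not amount to a test that the two differ: the first slope may be positive but imprecise, and the second may contain the same background gain. The children are of kindergarten age and Treatment 2 lasts 5-12 weeks, so some background gain is plausible. At stake is the learning claim for half of the taught words (30 of 60) and for one of the two treatment periods.

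**Working it through.** The documents state no sample size, alpha, effect size or SD for this analysis, so there is no planned figure to reproduce.

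**Step 1. Words left as controls (Summary of the Design).** 60 tested - 30 taught in Treatment 1 - 30 taught in Treatment 2 = 0.

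**Step 2. What each phase offers.**

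| Phase | Set 1 | Set 2 | Comparison available |
|---|---|---|---|
| Treatment 1 | taught | untaught | Set 1 against Set 2, same time, same child |
| Treatment 2 | already taught, maintenance | taught | Set 2 against its own Treatment 1 course only, at a different time |

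**Step 3. How a lone slope behaves under background gain.** All inputs here are assumptions: n children; background gain d per phase in units of the between-child SD of slopes; no treatment effect; two-sided 5% Wald test against zero. The rejection probability is

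R = 1 - Φ(1.96 - d√n) + Φ(-1.96 - d√n).

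With equal background gain in both phases and independent estimates, the pattern of a non-significant then a significant slope has probability (1 - R) × R.

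| n | Quantity | d = 0.1 | d = 0.2 | d = 0.3 | d = 0.5 |
|---|---|---|---|---|---|
| 20 | R | 0.073 | 0.145 | 0.269 | 0.609 |
| 20 | pattern | 0.068 | 0.124 | 0.196 | 0.238 |
| 40 | R | 0.097 | 0.244 | 0.475 | 0.885 |
| 40 | pattern | 0.088 | 0.185 | 0.249 | 0.101 |
| 60 | R | 0.121 | 0.341 | 0.642 | 0.972 |
| 60 | pattern | 0.106 | 0.225 | 0.230 | 0.027 |

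Example, n = 40, d = 0.3: d√n = 1.897; R = 1 - Φ(0.063) + Φ(-3.857) = 0.475; pattern = 0.525 × 0.475 = 0.249. At d = 0, R is 0.05 and the pattern 0.048.

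The two-part criterion is thus safer than the lone slope, because a large drift would usually show up in Treatment 1. At moderate drift it can still be met far more often than 5% of the time with no treatment effect.

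**Step 4. The direct contrast.** Take the Set 2 slope in Treatment 2 minus the Set 2 slope in Treatment 1. If background gain is equal in both phases it cancels, and the test rejects 5% of the time at any d. For equally precise slopes with correlation ρ, its SE relative to one slope is √(2(1 - ρ)): 1.41 at ρ = 0, √1.4 = 1.18 at ρ = 0.3, and 1.00 at ρ = 0.5. At n = 40 and a true effect of 0.5 SD, power is 61%, 76% and 89% respectively. The single slope has 89% with no background gain.

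**Step 5. Is the contrast like for like?** Not fully, for two reasons.

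- Interim tests in Treatment 1 are described for Set 1 only, so the Set 2 slope in that phase appears to rest on two points against three in Treatment 2. The extra point is an interim definition test given with pictures in view.
- Treatment 2 lasts 5-12 weeks, a range of 12/5 = 2.4-fold. If a child's two phases differ in length, background gain per phase may differ too.

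**The case against.** The strongest reply is that the plan makes one joint prediction for the same words in the same child, flat while untaught and rising while taught, and fits separate slopes to show it. Set A and Set B are randomized to first or second position. That stands, and it rules out several stronger readings.

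- A reader might infer that the plan ignores its own comparator, or that the Treatment 2 evidence is uncontrolled. The sentence containing the Treatment 2 criterion begins with the Treatment 1 expectation for Set 2. The comparator is modelled and interpreted; only the test of difference is unstated. The control is non-concurrent, not absent.
- A reader might infer that earlier testing of Set 2 words inflates the Treatment 2 slope. By the start of Treatment 2 each word has been tested three times, but the third test is the first point of that slope. Gains already made by then raise the baseline, not the slope. The documents do not say how retest gain is spread over time.
- A reader might put a figure on the drift share. With assumed counts of 1.5 to 2 words untaught and 2 to 6 taught, it is ln(2/1.5)/ln(6/2) = 0.288/1.099 = 26% on the log scale but 0.5/4 = 12.5% on the count scale. The documents support neither.

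It is also fair to say that the test against zero is inferred. The final time coding is in Table 7, which is not in the text available for this review, and a set-by-phase term may have been tested. The prose still states no such test, and two separate significance statements do not supply one.

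**Conclusion.** The concern holds as a gap in the stated inference. It affects 30 of the 60 taught words and the learning claim for Treatment 2. Three facts are documented: no never-taught words remain in that phase, Set 1 then serves only to show maintenance, and no test of the difference between the two Set 2 slopes is stated. The size of any background gain is unknown. The rejection rates above depend on assumed n, d, alpha, independence and equal drift; they show the mechanism and do not estimate what happened in this trial.

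A reader might go further and infer that the reported learning is unfounded or the dose conclusion biased. The documents support neither. Treatment 1 has concurrent untaught words. The main question, the effect of dose and dose frequency, compares randomized arms, where shared background gain largely cancels, although differing durations may keep it from cancelling completely.

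**What to change.** 1. Base the Treatment 2 learning claim on the within-child contrast: Set 2 slope in Treatment 2 minus Set 2 slope in Treatment 1, with its confidence interval.
2. Repeat it on the standard definition tests alone: the change from 2-week post-Treatment 1 to immediate post-Treatment 2, minus the change from pre-treatment to immediate post-Treatment 1. This leaves out the picture-supported interim test.
3. Use the day-coded model as a sensitivity analysis for differing phase lengths. The plan says this coding was evaluated and fitted less well than the categorical one, so it should support the main result and not replace it.
4. State that concurrently controlled evidence of learning comes from Treatment 1 (Set 1 against Set 2), and that the Treatment 2 control is non-concurrent.
5. Because the document already reports results, label the contrast as added afterwards if it was not part of the original analysis.

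Cost: item 1 needs one further estimate from slopes already in the model; items 2 and 3 each need another fit. The interval widens. The SE is about 1.4 times that of one slope if the two slopes are equally precise and uncorrelated, less if they are positively correlated, and possibly more if the Treatment 1 slope is less precise, as its apparently fewer test points suggest.

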Official Title: Interactive Book Reading to Accelerate Word Learning by Children with SLI

Grant #: R01DC012824

NCT#: NCT01829360

Date: October 18, 2019

Purpose. The goal was to determine whether interactive book reading outcomes for children with SLI were affected by manipulation of dose (i.e., the number of exposures to the target word during a book reading session) and dose frequency (i.e., the number of repeated book reading sessions) and whether pre-treatment factors predicted treatment response variation.

Participant Selection. Kindergarten children are recruited through community language screenings, referrals from speech-language pathologists, or advertisements. At first contact with an interested family, an informed consent document and background questionnaire are provided. The background questionnaire gains information about demographic characteristics of the child/family and assesses some of the inclusionary/exclusionary criteria.

Exclusionary Criteria: a child is excluded from participation if he/she:

- (1) speaks more than one language, as determined by background questionnaire;
- (2) has a health history indicating neurologic or other disorders that would exclude a diagnosis of SLI (e.g., autism), as determined by background questionnaire.

[figure not shown]
Inclusionary Criteria: children will

- (1) be at least 5-years-old and in/eligible for kindergarten, as determined by background questionnaire;
- (2) pass a hearing screening;
- (3) have nonverbal IQs at or above the 16th percentile on the *Reynolds Intellectual Assessment Scale-2* to rule out cognitive deficits;
- (4) have a Core Language Score at or below the 9th percentile (standard score = 80, 1.3 SD below mean) on the *CELF-4* to document language impairment;
- (5) score at or below the 9th percentile (standard score = 6) on the semantics subtest of the *DELV* or the word classes subtest of the *CELF-5* to document a vocabulary deficit. Score cut-offs are based on classification accuracy reported in the manuals (when reported).

[figure not shown]
Procedural flowchart. Is shown in the following multi-page figure. Each major procedure is described below.

[figure not shown]
Standardized Testing: Once informed consent is attained, standardized tests are administered to assess inclusionary criteria and gain additional information to further characterize the participants and potentially predict their performance in treatment.

[figure not shown]
- Pre-Session 1

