Primary outcome measure: Definition task. As in our prior preliminary clinical trial (Storkel, Voelmle, et al., 2017), the primary outcome measure was a definition task. We chose a definition task for two reasons: (1) to afford comparison to our past research with this treatment to determine whether continuing changes to the treatment improve outcomes; (2) to ensure that the treatment is helping children establish the rich word knowledge needed to support a variety of linguistic tasks. Although this task sets a high bar for word learning, our past research shows that it is sensitive enough to detect changes between different treatment conditions. The definition task was administered before treatment, immediately following the conclusion of each treatment, and 2 weeks following the conclusion of each treatment

Research assistants administer the task across two sessions with 15 Set A and 15 Set B words tested in each session. For each word, the child received the prompt, “Tell me what [word] means.” Prompts were pre-recorded and presented with computer software so that pronunciations of the words were consistent across tasks. Children’s responses were audio recorded and transcribed for later scoring. The children first hear three practice words (*bed, ball, candy*), which were words likely to be known by them to ensure that they understood the task. Then, the 30 target words are presented in random order along with familiar words ($n = 10$, e.g., *chair, teacher, apple*). In terms of training the testers, all testers are shown how to use the computer software and the recording device. Testers practice administering the definition test to other trained testers until they are comfortable with the equipment and protocol. Testing script is available at https://asha.figshare.com/articles/Dose_Dose_Frequency_Storkel_et_al_2019_9745181 *Supplemental Material S7 Testing script.*

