The definition scoring procedures from our prior preliminary clinical trial (Storkel, Voelmle, et al., 2017) are used. In the prior study, the research team followed the procedures of McGregor, Oleson, Bahnsen, and Duff (2013) and consulted dictionaries to create a scoring rubric that listed common elements of an accurate and complete definition for each word (e.g., pouted = negative emotion + lips/face). Possible scores were: 0 points for an incorrect or absent definition (e.g., pouted = face), 1 point for an appropriate use of the word in a sentence (e.g., pouted = pouted because you don’t want to eat and your mom makes you) or for a vague definition (e.g., pouted = cry), 2 points for a conventional definition containing at least one critical element but lacking other critical elements (e.g., pouted = mad), and 3 points for a complete and accurate definition including all critical elements (e.g., pouted = feel mad and push your lips out). Two raters independently score each response following the rubric guidelines. The raters compare their scores and resolve disagreements through consensus.

In the analyses, children’s definitions scored as 2 or 3 (i.e., a partially or completely accurate definition) are counted as correct and definitions scored as 0 or 1 (i.e., incorrect definition, absent definition, correct use of a word in a sentence, or vague definition) are counted as incorrect. This was done to afford comparison to prior studies (Justice et al., 2005; Storkel, Voelmle, et al., 2017).

Secondary outcome measure: Interim definition. Learning also is tracked during treatment. The research assistant who provides the treatment prompts children to provide definitions or name the target words at four points during each treatment. The words are assessed in a fixed order while the child views the pre-reading pictures for each word. The research assistant asks, "What does [word] mean?". Specific feedback is not provided but the correct definition always is provided after the child's response regardless of the accuracy of the response. This is shown in the scripts at

https://asha.figshare.com/articles/Dose_Dose_Frequency_Storkel_et_al_2019_9745181. Definition responses were scored by two independent raters unaware of children's treatment assignment following the procedures described above.

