Results. Results are reported fully in Storkel, H. L., Komesidou, R., Pezold, M. J., Pitt, A. R., Fleming, K. J., & Romine, R. S. (2019). The impact of dose and dose frequency on word learning by kindergarten children with developmental language disorder during interactive book reading. *Language, Speech, and Hearing Services in Schools*, 50, 518–539. https://doi.org/10.1044/2019_LSHSS-VOIA-18-0131 - open access

Summary of Results. Results showed that children with DLD learned a significant number of words during treatment regardless of the dose and dose frequency format, but that significant forgetting of newly learned words occurred in all formats once treatment was withdrawn. Individual differences in word learning were related to CELF Core Language and CELF Understanding Spoken Paragraphs scores.

Conclusion. When administered at an adequate intensity, variation in the dose and dose frequency of interactive book reading does not appear to influence word learning by children with DLD. Although interactive book reading continues to show promise as an effective word learning intervention for children with DLD, further development is needed to enhance the effectiveness of this treatment approach.

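### A Gaussian model of log counts is called a negative binomial GLMM, and no rule covers a child who defines no words; with low counts the slope sizes depend on that rule

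*Combined protocol and SAP*

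**What the plan says.** The Data Analysis Strategy section describes the only model given for the primary outcome: "A series of multilevel longitudinal models were evaluated using SAS Proc Mixed", applied to the number of Set 1 and Set 2 words defined at seven test points. Because the outcome is a count, the plan takes logs: "natural log of the words defined was modeled resulting in a model equivalent to a generalized linear mixed model with a negative binomial link". Fixed effects are tested by Wald tests, and "the significance of random effects was evaluated using likelihood ratio tests and information criteria between models with the same fixed effects".

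The count runs from 0 to 30 for each word set. In the scoring rules for the primary outcome, scores of 2 or 3 "are counted as correct and definitions scored as 0 or 1" as incorrect. A child who gives only absent, vague or sentence-use answers therefore scores zero for the set. No section names an added constant, an exclusion, or any other treatment of a zero.

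Several features make zeros plausible. One entry criterion is there "to document a vocabulary deficit". The words are tested before any teaching. During Treatment 1, "Set 2 words have not yet received treatment and serve as untreated control words" (Summary of the Design). On the task itself the plan says: "Although this task sets a high bar for word learning, our past research shows that it is sensitive enough to detect changes". That sentence points to low scores and also claims sensitivity.

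**The concern.** There are two faults.

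- **The model is misdescribed.** The reader is told that a count model was fitted, but the procedure and transformation named are those of a Gaussian model. Negative binomial is a distribution; the usual link in such a model is the log.
- **The outcome is undefined at zero.** Read literally, a record with no word defined drops out. Otherwise a constant was added that the document does not state. Dropping is selection on the outcome itself, so the mixed model's usual tolerance of missing records does not protect against it.

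The first point of the Treatment 1 slope is pre-treatment, when zeros are most likely, so the zero rule acts where that slope is anchored. If counts are low, three results depend on it: the size of non-zero slopes, the contrast between treated and control words, and relations with baseline ability. The last matters because the Summary of Results reports that "Individual differences in word learning were related to CELF Core Language" scores.

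**Working it through.** **Inputs from the document.** Proc Mixed; natural log of the count; 30 words per set; only scores of 2 or 3 count; Treatment 1 slope over pre-treatment, 36 exposures and immediate post-treatment. The document gives no mean count, share of zeros, sample size, alpha or slope, so there is no figure of the plan's own to reproduce.

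**Equivalence.** Proc Mixed on ln Y fits E[ln Y] = Xβ + Zu with constant residual variance. A negative binomial GLMM fits ln E[Y | u] = Xβ + Zu, with a variance that increases with the mean. E[ln Y] and ln E[Y] differ whenever Y varies, and the first does not exist if P(Y = 0) > 0.

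**A case that can be checked by hand.** Take Y ~ Binomial(30, p) with no variation between children and means of 1 then 4 words.

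- Zeros at baseline: (29/30)^30 = 0.362.
- Target: ln(4/1) = 1.386, a ratio of 4.0.
- Change in E[ln(Y+1)]: 0.955, a ratio of exp(0.955) = 2.60.
- Change in E[ln(Y+0.1)]: 1.831, a ratio of exp(1.831) = 6.24.
- Change in E[ln Y | Y > 0]: 0.939, a ratio of exp(0.939) = 2.56.

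**With variation between children.** Assume logit p = a + s·z, with z standard normal and s = 0.5 or 1, and a solved for each assumed mean. The estimated ratio is exp(E[ln(Y_post + c)] − E[ln(Y_pre + c)]), or the same on Y > 0 if zeros are dropped. Ranges cover the two values of s.

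| Assumed means | True ratio | Zeros at baseline | Dropped | +1 | +0.5 | +0.1 |
|---|---|---|---|---|---|---|
| 1 to 6 | 6.0 | 40-49% | 2.9-3.5 | 3.3-3.6 | 4.5-4.9 | 9.1-9.8 |
| 2 to 6 | 3.0 | 18-30% | 2.2-2.5 | 2.3-2.4 | 2.8-2.9 | 4.1-4.3 |
| 5 to 10 | 2.0 | 2-9% | 2.0-2.1 | 1.9-2.0 | 2.1-2.2 | 2.2-2.6 |
| 1 to 1 | 1.0 | 40-49% | 1.0 | 1.0 | 1.0 | 1.0 |

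**Fitted three-point slope.** A random-intercept model on log counts from 40,000 simulated children (1 to 6 words) gave ratios, as exp(2 × slope), of 3.7-3.8 with zeros dropped, 3.3-3.6 with +1, 4.5-4.9 with +0.5 and 9.1-9.9 with +0.1. A binomial GLMM gave 6.0, as it should, because the data were simulated from that model. Dropping zeros removed at least one of the three records for 46-56% of children (1 to 6), 23-37% (2 to 6) and 3-12% (5 to 10).

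**A second simulation under different assumptions.** It used overdispersed counts, 30 children, a baseline of 0.6 words before random effects, 57% zeros at baseline and a true log slope of 0.80. The log-count model gave 0.40 (dropped), 0.41 (+1), 0.54 (+0.5), 0.85 (+0.1) and 1.32 (+0.01). A negative binomial GEE gave 0.79. Mean Wald z for the log-count fits was 3.8 to 5.7.

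**Flat slopes.** With an assumed 30 children and a constant mean of 1 or 2 words, type I error at a nominal 5% was 4.8-5.9% with a constant added and 5.6-6.8% with zeros dropped.

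**Baseline ability.** Compare children going from 1 to 4 words with children going from 2 to 8, both a fourfold rise. The ratio of their estimated ratios runs from 0.97 to 1.47 across zero rules (s = 0.5), or from 1.20 to 1.40 (s = 1).

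**The case against.** The strongest reply is that the trial's main question is barely touched. The Purpose section asks about dose and dose frequency, the arms are randomized, and the reported conclusion is that format made no difference. Null arm contrasts with equal baselines are not biased in expectation. The plan's stated expectations are about significant versus non-significant slopes. Flat slopes keep close to nominal error, and a strong slope stayed clearly significant under every zero rule. This stands: the evidence is about the size of slopes and contrasts, and it does not show that the trial's main significance findings are wrong.

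The counts are also assumed. At means of 10 to 15 words (true ratio 1.5) the four rules give 1.50-1.57 (s = 0.5) or 1.57-1.70 (s = 1), so the zero rule would matter little. This stands too. So does a limit on direction: dropping zeros or adding 1 understates growth only at low means. At 5 to 10 words, dropping gives 2.0-2.1 against 2.0.

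It can be said that the ratio of means is not a target the plan sets. But a log-link negative binomial model estimates exactly that ratio, and the plan claims equivalence to such a model.

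A binomial model does not remove dependence on scale: for 1 to 4 versus 2 to 8 words its odds-ratio contrast is 1.17-1.24 rather than 1. That is fair, but its scale is stated and needs no arbitrary constant. Finally, the cited results article may give a zero rule. It could not be consulted, and this document gives none.

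**Conclusion.** The concern holds. The equivalence statement is wrong whatever the data. The stated primary model is undefined at a score that the scoring rules allow, and no rule fills the gap.

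The numerical consequence is conditional on low counts. It is large at a baseline mean of about 1 word (a true sixfold rise estimated as 2.9 to 9.8), moderate at 2 words (threefold estimated as 2.2 to 4.3), and small at 5 words unless the added constant is tiny. All of this rests on assumed means, an assumed spread between children and, for the error rates, an assumed 30 children. The full seven-point, two-set model was not fitted. Whether zeros were frequent in this trial, and how they were handled, cannot be determined from the document.

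**What to change.** Delete the equivalence statement. Fit the untransformed counts with the same piecewise time terms in Proc GLIMMIX. Use either a binomial out of 30 (events/trials) with child random effects and an overdispersion term, or an actual negative binomial with log link. Both accept zeros without a constant. Use METHOD=LAPLACE or QUAD, so that the planned likelihood ratio tests and information criteria rest on a true likelihood.

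Report the number of zero counts by word set and test point, and model-based words defined out of 30. If that table shows few zeros, the numerical part of the concern largely goes away. If the log-count model is kept for comparison, state its zero rule and label it a sensitivity analysis.

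The cost is a re-run of the model series on the same data in a different SAS procedure, estimates expressed as odds or rate ratios, and one added table. No new data are needed. Where results are already published, the re-run can be reported alongside them.
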